## 4 Study Endpoints

### 4.1 Primary Endpoint

The primary endpoint is the annualized change in new HO volume as assessed by low-dose, WBCT (excluding head) compared to untreated subjects from the NHS over 24 months.

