## 8 Statistical Considerations

### 8.1 General Considerations

This study is intended to assess whether a chronic dosing regimen, combined with higher doses during times of flare-ups, will reduce new HO formation. As this is an open-label study with no randomized control group, use of subject data from Study PVO-1A-001 (Natural History Study [NHS]) over 24 months will form the basis for a control arm. Therefore, the primary comparison of outcomes from this study will be made to data collected from the NHS in order to determine whether the chronic/flare-up regimen provides benefit over the untreated condition (data from the NHS). In addition, the primary efficacy analysis will be restricted to MOVE subjects who have the R206I mutation and who have not previously been treated with palovarotene. These restrictions increase the validity of the comparison to the NHS historical control which only enrolled subjects with the R206I mutation and no previous palovarotene exposure.

This section contains a brief overview of the statistical analyses planned for this study. Details of all planned analyses will be provided in the formal statistical analysis plan (SAP).

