1.6 Objectives

1.6.1 Primary Objectives

- To evaluate the efficacy of palovarotene in decreasing heterotopic ossification (HO) in adult and pediatric subjects with FOP as assessed by low-dose, whole body computed tomography (WBCT), excluding head, as compared to untreated subjects from Clementia's FOP natural history study over 24 months.
- To evaluate the safety of palovarotene in adult and pediatric subjects with FOP.

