2.1.3 Efficacy Endpoints

Primary Efficacy Endpoint

The primary efficacy endpoint is the annualized change in new HO volume as assessed by low-dose, WBCT, excluding head. The annualized change in new HO volume will be compared between treated and untreated subjects. WBCT scans are performed at baseline, Month 12,

Month 24 and Month 36 in the NHS and at baseline, Month 6, Month 12, Month 18 and Month 24 in the MOVE Trial. WBCT scans may also be performed at the time of early study discontinuation.

As described in the MOVE Trial and NHS Independent Review Charter, HO volume is assessed by two independent readers blinded to study and timepoint, with adjudication by a third independent reader. HO volume is measured by body region with the baseline scan. The following 9 anatomical regions will be used to describe HO location:

- Right chest, neck, shoulder through mid-humerus
- Left chest, neck, shoulder through mid-humerus
- Mid Torso: torso below shoulder regions and above iliac crests
- Right arm: mid-humerus through hand
- Left arm: mid-humerus through hand
- Right hip: iliac crest, hip through mid-femur
- Left hip: iliac crest, hip through mid-femur
- Right lower leg: mid-femur through foot
- Left lower leg: mid-femur through foot

In post-baseline scans, the presence of new HO within each body region and, if present, the HO volume within the body region, are measured. The primary efficacy analysis described in [Section 0](#) models the number of body regions with new HO compared to the previous scan and the volume of new HO within each body region with new HO compared to the previous scan as the unit of measurement.

Note that the primary endpoint includes annualized HO based on the new HO observed up to Month 24 in MOVE and up to Month 36 in NHS. The sponsor believes that the new HO observed between Month 24 and Month 36 in NHS is relevant and that annualization is sufficient to protect against bias. Sensitivity analyses to assess impact of differences in length of follow-up between NHS and MOVE are described in [Section 2.4.4](#).

The primary efficacy endpoint, as well as the secondary endpoints that depend on the efficacy imaging, will not be summarized in the descriptive analysis to be conducted before the first formal interim efficacy analysis, due to the ongoing nature of the blinded reads.

Secondary Efficacy Endpoints

The following secondary efficacy endpoints will be assessed:

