The primary efficacy endpoint is the annualized change in new HO volume (as assessed by WBCT). The change in new HO volume is calculated by summing the increase in HO volume across all body regions for which new HO has occurred where the increase in HO volume per region is defined as the square-root of the volumetric increase in that region. The square-root transformation is used to reduce the influence of outliers. Transformation of volumetric changes has been used in related contexts. For example, a log transformation has been used to model volumetric increases in the kidneys of subjects with autosomal dominant polycystic kidney disease^{1,2}. The change in new HO volume is modeled using a Bayesian compound Poisson distribution. The Bayesian compound Poisson distribution assumes that the change in new HO volume can be modeled as a compound distribution of the number of body regions with new HO, K , and the new HO volume per region where new HO has occurred, Z . The number of body regions with new HO in subject i for WBCT scan j with duration w_{ij} (the time between scan j and the previous scan) is distributed as

$$K_{ij} \sim \text{Pois}(\lambda_{i,j} * w_{ij} * \theta_{1,t(ij)});$$
$$\log(\lambda_{i,j}) = \log(\lambda_i) + \beta_1 X_{1,i} + \beta_2 X_{2,i,j}$$

The subject-level rate λ_i follows a gamma distribution and accounts for potential correlation in measurements from the same subject; $t(ij)$ is an indicator function equal to 1 if the subject was on treatment at the time of the j th WBCT scan and 0 if the subject was not on treatment. Therefore, the marginal distribution of the number of body regions with new HO follows a negative binomial distribution, which requires much less restrictive assumptions than a Poisson distribution and does not tend to result in an underestimate of the variance.

Letting $\theta_{1,0} = 1$, the variable $\theta_{1,1}$ is the multiplicative effect of palovarotene treatment on the rate of body regions with new HO. Covariates are included in the analysis of the number of body regions with new HO to adjust for potential explained differences in the rate of new HO based on the subject's sex, $X_{1,i}$, and age at time of scan, $X_{2,i,j}$. Age at the time of scan is represented as a factor variable with 0 for <18 years old and 1 for ≥ 18 years old. Covariate effects $\exp(\beta_1)$ and $\exp(\beta_2)$ are multiplicative effects of sex and age on the rate of body regions with new HO.

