- Restriction to subjects contributing follow-up for both the NHS and MOVE Trial: This analysis will use the wLME analysis method on the subset of the MOVE subjects who transitioned from the NHS and have annualized rates of new HO for both studies. Baseline HO volume divided by age will be the only covariate included in the model, in addition to the factor identifying the study of origin.
- As requested by regulatory agencies, a matched pairs analysis – including subjects who participated in either MOVE or NHS but not both studies – was performed. Caliper-matching used propensity scores described in this SAP. The analysis used a paired t-test.

To assess impact of differences in length of follow-up between NHS and MOVE:

- Analysis restricting subjects to specific durations of follow-up: The WBCT dataset will be restricted to observations associated up to 1-year – interpreted as assessments within the first 15 months of study participation (i.e., midway between Month 12 and Month 18 for MOVE) – and, separately, with up to 2-years of follow-up – interpreted as assessments within the first 27 months of study participation. The analysis method will be wLME.

To assess impact of missing data in MOVE:

- Missing data sensitivity analysis using a tipping point approach: Subjects who discontinue the MOVE study will have volume of new HO imputed using the wLME-modeled treatment effect. The multiple imputations will be scaled to induce 0%, 25%, 50%, 75%, and 100% reductions in the palovarotene treatment effect. The 0% corresponds to subjects who discontinue the MOVE Trial having the same distribution for number of body regions with new HO and change in HO volume per region as the MOVE subjects who did not discontinue; and 100% corresponds to subjects who discontinued the MOVE Trial having the same distributions as the NHS subjects. Missing data will be imputed for the visits in MOVE that were either missed or would have been missed due to study discontinuation prior to December 4, 2019 / January 24, 2020. Analyses in which subjects who discontinue the NHS have volume of new HO imputed may also be considered, while noting that the majority of subjects who discontinued NHS did so to enroll in an interventional study, e.g., MOVE or less frequently, Study PVO-1A-201.

To assess robustness of efficacy signal against choice of wLME as post-hoc analysis:

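### The primary endpoint is set at 24 months, but the SAP takes control data to Month 36 and never fits the Bayesian model to the 24-month comparison

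*SAP*

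**What the plan says.** Three places fix the window at 24 months for the control as well as for MOVE.

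- Protocol 4.1 defines the primary endpoint as the annualized change in new HO volume "compared to untreated subjects from the NHS over 24 months".
- Protocol 8.1 states that "use of subject data from Study PVO-1A-001 (Natural History Study [NHS]) over 24 months will form the basis for a control arm".
- SAP 1.6.1 repeats the objective "as compared to untreated subjects from Clementia's FOP natural history study over 24 months".

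SAP 2.1.3 then gives the two studies different windows: "annualized HO based on the new HO observed up to Month 24 in MOVE and up to Month 36 in NHS". As its reason it offers the sponsor's belief that the third-year NHS data are relevant and that "annualization is sufficient to protect against bias". The section points to sensitivity analyses in SAP 2.4.4 on differing lengths of follow-up.

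On the primary analysis, SAP 2.4.4 says: "The change in new HO volume is modeled using a Bayesian compound Poisson distribution". Its item on differing lengths of follow-up restricts the data to the first 15 months and, separately, the first 27 months of participation, and ends: "The analysis method will be wLME".

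**The concern.** Dividing by time makes two unequal windows comparable only under two conditions. The rate of new HO must be stable over follow-up, and the subjects who remain to Month 36 must resemble those who do not.

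The SAP gives some reason to check both. SAP 1.10.1 says that age may matter for new HO, while the model separates only under 18 from 18 and over. SAP 2.4.4 notes that "the majority of subjects who discontinued NHS did so to enroll in an interventional study", so those scanned at Month 36 may be a selected group.

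The untreated rate is the denominator of gamma, the efficacy ratio. If third-year NHS data differ from the first two years, gamma moves, and nothing planned would show by how much under the model that carries the primary result. The reported primary also answers a slightly different question from the one in the protocol, and the change is not listed as one.

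**Working it through.** **1. Is the 24-month contrast estimated with the Bayesian model anywhere?**

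- The lead-in to the sensitivity analyses in SAP 2.4.4 says that both methodologies will be used, but only as each item describes. The follow-up item describes wLME alone.
- No row of SAP Table 8 caps NHS at Month 24. The row for the square-root Bayesian model on all timepoints is labelled as the protocol-specified primary analysis, although it has no such cap.
- SAP 1.9 and 1.10 list changes from the protocol and between SAP versions. The Month 36 window is not among them. The V1.2 entry mentions added timepoints only for secondary and exploratory endpoints.
- In SAP 2.1.3 the CAJIS, FOP-PFQ and PROMIS endpoints run through Month 24 in both studies, so the windows are aligned there but not for the primary.

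The answer is no.

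**2. The plan's own follow-up figure**

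SAP 2.4.4 and protocol 8.5.2.1 give 317.5 years of expected follow-up: 45 × 1.5 + 45 × 2.0 + 80 × 2.0 = 67.5 + 90 + 160 = 317.5. It reproduces exactly. The NHS part is 157.5 years and contains nothing beyond Month 24. A 24-month cap therefore matches the basis on which the trial was planned.

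**3. How far could a third year move the result?**

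Inputs:
- Base: 157.5 NHS years, from step 2.
- k: number of NHS subjects adding one further year. This is not given. I assume 20 to 45, because only 45 subjects reach Month 24 on this base.
- r: third-year rate relative to the earlier rate. This is also an assumption: 0.7 to 1.3, then 0.5 to 1.5.

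Control rate relative to its 24-month value: C = (157.5 + k × r) / (157.5 + k).

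With the MOVE side unchanged, gamma is multiplied by 1/C.

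| k | share of NHS time, k/(157.5 + k) | r | control rate shift | gamma shift |
|---|---|---|---|---|
| 20 | 20/177.5 = 11.3% | 0.7 | 171.5/177.5: −3.4% | +3.5% |
| 20 | 11.3% | 1.3 | 183.5/177.5: +3.4% | −3.3% |
| 45 | 45/202.5 = 22.2% | 0.7 | 189/202.5: −6.7% | +7.1% |
| 45 | 22.2% | 1.3 | 216/202.5: +6.7% | −6.3% |
| 20 | 11.3% | 0.5 | 167.5/177.5: −5.6% | +6.0% |
| 20 | 11.3% | 1.5 | 187.5/177.5: +5.6% | −5.3% |
| 45 | 22.2% | 0.5 | 180/202.5: −11.1% | +12.5% |
| 45 | 22.2% | 1.5 | 225/202.5: +11.1% | −10.0% |

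At r = 1 there is no shift. The calculation pools crude person-time. The hierarchical model does not weight the data this way, so the table indicates scale and does not predict the fitted gamma.

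**4. What the model already absorbs**

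In SAP 2.4.4 the count of regions with new HO is scaled by scan interval and has a subject-level rate, sex, and age at scan in two classes. If those who stay to Month 36 simply have higher or lower rates, the subject term takes up part of that. The volume part has a region term and a treatment term but no subject or age term, so it has no such protection.

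**The case against.** The best defence is that the SAP states the asymmetry openly and plans a check written for it. That check uses wLME, which is not a marginal method here. Untransformed, it was the original protocol's primary analysis, and the SAP now calls it the alternative analysis of primary interest. The SAP also reports that Bayesian and wLME results agreed at the second and third interim analyses. A reader might infer that the 24-month contrast is not estimated at all. That is too strong: it is estimated, but with wLME only. The check still does not settle the matter for the Bayesian result. wLME uses one longest-follow-up observation per subject per study, can keep negative changes when untransformed, and does not estimate gamma.

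A second defence is that unequal follow-up is not bias in itself. NHS Month 0 is study entry rather than a point in the disease course, and many MOVE subjects' treated time follows their NHS time. The statement about NHS leavers gives their reason for leaving and does not say that their HO rate differed. This stands. The documents do not support a claim that the Month 36 window biases the result, or in which direction.

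Third, since futility was crossed at the second interim analysis, later efficacy analyses apply no success or futility thresholds, so no formal decision turns on this window. That is correct, and it limits the weight of the point. The estimates still go into the clinical study report and the marketing applications.

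**Conclusion.** The point holds as a gap in estimation and in documentation. The protocol-defined 24-month comparison is missing under the named primary model and under its untransformed version, and the wider control window is not recorded as a change.

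On the assumptions above, the crude control rate could move by about 3% to 7% either way, with gamma moving by at most about −6% to +7%. Under the wider range of third-year rates, the figures are about 6% to 11%, and −10% to +12.5%. These depend on an assumed 20 to 45 third-year subjects and assumed rate ratios, since the documents give neither Month 36 counts nor rates by year.

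A reader might infer larger shifts by letting more than 45 subjects contribute a third year. The 157.5-year base does not allow that, because only 45 of its subjects reach Month 24. A reader might also conclude that the Month 36 analysis should be demoted to a sensitivity analysis. Exchanging roles after unblinding is debatable, and it is not needed to close the gap.

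**What to change.** Fit the Bayesian compound Poisson model, with and without the square root, with NHS assessments limited to the SAP's own 27-month window. Report each run beside its Month 36 counterpart and label it as the protocol-defined 24-month analysis. Add the Month 36 window to the SAP's list of modifications as a departure from the protocol, and give the number of NHS subjects with a Month 36 scan.

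This has to be requested explicitly. SAP 3.3 does not plan to rerun interim-report analyses for the final report, and SAP 2.4.4 plans no Bayesian analyses after database lock.

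The cost is a re-run of existing code and a slightly wider interval for that run, since it gives up the third-year control follow-up. Truncation does not remove selective departure from NHS before Month 24. The planning case already has 45 of 90 subjects ending at 1.5 years and about half of the 90 entering MOVE, so that limitation should be stated with the result.

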### 4.2 Secondary Endpoints

The following secondary endpoints will be assessed in Parts A and B:

1. The proportion of subjects (key secondary endpoint) with any new HO.
2. The change from baseline in the number of body regions with new HO.
3. The proportion of subjects reporting flare-ups.
4. The flare-up rate per subject-month exposure.

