The primary efficacy analysis comparing the annualized change in new HO volume between subjects treated with palovarotene and untreated subjects is performed by calculating the ratio of the annual mean change in HO volume in palovarotene treated subjects to untreated subjects using the Principal FAS and assuming missing at random. Using the Bayesian compound Poisson model described above, this ratio is calculated as the treatment effect on the rate of body regions with new HO,  $\theta_{1,1}$ , multiplied by the treatment effect on new HO volume conditional on new HO occurring,  $\theta_{2,1}$ , expressed as  $\gamma = \theta_{1,1} * \theta_{2,1}$ . Random samples generated via Gibbs sampling from the posterior distribution of  $\theta_{1,1}$  and  $\theta_{2,1}$  will be used to compute the posterior probability that  $\gamma < 1$  to determine statistical significance. The primary efficacy analysis described above will be repeated without the square-root transformation. Additional supportive analyses including the weighted mixed linear effect (wLME) analysis with and without the square-root transformation will also be performed.

Approximately 80 palovarotene-naïve subjects with the R206H ACVR1 mutation will be enrolled into the current study and will be followed for 2 years in Part A. There will be three early interim efficacy analyses and one final analysis in Part A. The first interim analysis will occur when 35 subjects complete 1 year of follow-up; the second and third interim analyses will occur when all subjects enrolled in the Principal EP have completed (ie, have WBCT data) 12 months and then 18 months of follow-up, respectively. The interim analyses will include the Month 6 WBCT results when that is the only observation available from a subject in the current study. While study success may be declared after one of the interim analyses or at the final analysis in Part A, all subjects will continue until completing 48 months of treatment.

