### **8.5.2.2 Secondary Efficacy Analysis**

The secondary efficacy endpoints will be analyzed using the Principal FAS and PPS populations. Treatment effect estimates will be generated for Part A, and overall for data obtained in Parts A and B.

The proportion of subjects with any new HO and the change in the number of body regions with any new HO will be analyzed using the Bayesian compound Poisson distribution used for the primary efficacy analysis. The variables in that model can be used to construct the hypothesis test for both of these secondary efficacy endpoints.

The proportion of subjects with any flare-ups and the flare-up rate per subject-month exposure will be analyzed using a Bayesian Poisson distribution.

The secondary efficacy endpoints will be summarized for the Supplementary FAS and PPS.

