1.3 Context for Version 1.2

This amendment is introduced after the third interim analysis. It introduces edits, including changes to existing analyses and additions of new analyses, to be included in the interim CSR for Study PVO-1A-301 (MOVE Trial) to be included in the palovarotene marketing authorization application for FOP.

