1.10.3 Statistical Modifications to the Statistical Analysis Plan, V1.2

SAP Version 1.2 introduces the following changes:

- Clarifies that drawing subject-level rates of body regions with new HO from a gamma distribution and then drawing from Poisson distributions using these subject-level rates implies that the marginal distribution of the number of body regions with new HO follows a negative binomial distribution, which requires much less restrictive assumptions than a Poisson distribution and does not tend to result in an underestimate of the variance.
- Notes that additional details of the operating characteristics of the Bayesian compound Poisson analysis, including its chance of producing erroneous conclusions and the reliability of treatment effect estimates, will be included in a separate simulation report.
- Clarifies the secondary and exploratory endpoint definitions to add timepoints at which the endpoints will be compared between NHS and MOVE.
- Clarifies the definitions of treatment-emergent AEs and post-treatment AEs.
- Removes summaries of retinoid-associated AEs, as they already appear in the AE tables.
- Clarifies that a listing of traumas leading to flare-up will be generated.
- Adds summaries of imaging performance, i.e., intra-reader agreement and inter-reader agreement, and quality metrics.
- Adds summaries of dosing compliance.
- Clarifies the wLME analysis method by adding pseudocode.
- Clarifies the methods used to prepare the dataset for application of the Bayesian compound Poisson analyses and square-root transformation, including the methods used to ‘zero out’ negative changes in HO volume.
- Clarifies the purpose, timing and conduct of the sensitivity analyses.
- Updates the list of subgroups to be studied to be consistent with feedback from FDA.
- Adds analyses for the HO-based secondary analyses and simplifies the analyses of the flare-up-based secondary endpoints.
- Adds summaries of growth velocity.
- Summarizes duration of flare-up treatment and duration of non-flare-up treatment, which are used in the summary of compliance.

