- The proportion of subjects with any new HO at Month 12 (key secondary endpoint).

- The number of body regions with new HO at Month 12.
- The proportion of subjects reporting flare-ups at Month 12.
- The flare-up rate per subject-month exposure through Month 24.

Note that only MOVE flare-ups with ≥ 2 symptoms will be included in the derivation of the proportion of subjects reporting flare-ups and flare-up rate per subject-month exposure. This will better align the MOVE derivation with the definition of flare-up in the NHS, which required > 1 symptom.

The secondary endpoints that depend on the efficacy imaging, i.e., the proportion of subjects with any new HO and the number of body regions with new HO, will not be summarized in the descriptive analysis to be conducted before the first formal interim efficacy analysis, due to the ongoing nature of the blinded reads.

Exploratory Efficacy Endpoints

The following exploratory efficacy variables will be assessed:

- Change from baseline in ROM assessed by CAJIS through Month 24 in MOVE and NHS.
- Change from baseline in physical function through Month 24 in MOVE and NHS, using age-appropriate forms of the FOP-PFQ.
- Change from baseline in physical and mental function for subjects ≥ 15 years old and mental function for subjects < 15 years old using age appropriate forms of the PROMIS Global Health Scale, through Month 24 in MOVE and NHS.
- Incidence and volume of catastrophic HO per year, i.e., new HO $> 50,000 \text{ mm}^3$; and new HO $> 30,000 \text{ mm}^3$ at Month 12 and Month 24.

ROM Assessed by CAJIS

Range of motion will be assessed using the CAJIS. The assessments will be performed on 12 joints (shoulder, elbow, wrist, hip, knee, and ankle on both the right and left sides), and three body regions (jaw, cervical spine [neck], and thoracic/lumbar spine). Each joint/region will be scored as: 0 = uninvolved; 1 = partially involved; and 2 = ankylosed/completely involved.

The CAJIS Total score will be calculated as the sum of the scores of all joints/regions and ranges from 0 (no involvement) to 30 (maximally involved).

The CAJIS Upper Extremities subscore will be calculated as the sum of the scores from six joints (shoulder, elbow, and wrist on both the right and left sides) and one region (cervical spine [neck]) and ranges from 0 (no involvement) to 14 (maximally involved).

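### The SAP sets the key secondary and two other secondary endpoints at Month 12; the protocol estimates them over Part A and over Parts A and B, and the change, made after unblinding, is logged as a clarification

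*SAP*

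**What the plan says.** **Protocol.** Section 4.2 introduces the secondary list with "The following secondary endpoints will be assessed in Parts A and B". The list contains the proportion with any new HO (key secondary), the number of body regions with new HO, the proportion reporting flare-ups, and the flare-up rate. No item carries a Month 12 limit. Section 8.5.2.2 adds: "Treatment effect estimates will be generated for Part A, and overall for data obtained in Parts A and B". It names the primary model's Bayesian compound Poisson distribution for the two HO endpoints and a Bayesian Poisson distribution for the two flare-up endpoints. The 24 months come from the length of Part A: in 8.5.2.1, subjects "will be followed for 2 years in Part A".

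**SAP.** Section 2.1.3 defines three of the four endpoints at one year. The key secondary reads "The proportion of subjects with any new HO at Month 12 (key secondary endpoint". The region count and the share of subjects with a flare-up are tied to the same visit; the latter reads "The proportion of subjects reporting flare-ups at Month 12". Only the flare-up rate is left to run to Month 24. Section 2.4.4 repeats the Month 12 label for the two HO endpoints. It applies an exact test to Month 12 incidence and a negative binomial regression to Month 12 counts. The flare-up proportion gets an exact test.

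**Dating.** SAP 1.10.3 (V1.2) records the change this way: "Clarifies the secondary and exploratory endpoint definitions to add timepoints at which the endpoints will be compared between NHS and MOVE". SAP 1.3 says of V1.2: "This amendment is introduced after the third interim analysis". SAP 1.4 puts the sponsor's unblinding to efficacy after the second interim analysis. SAP 1.9, which lists modifications to the protocol's statistical section, does not mention the time point.

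**The concern.** A subject whose first new HO or first flare-up comes after Month 12 counts as an event over Part A but not in a Month 12 proportion. The two documents therefore define different quantities under the same endpoint name, and the choice between them was made with the efficacy data open. The trial is open-label with an external control, and its interim report supports marketing applications (SAP 3.3). A reader of the key secondary should be able to see which time frame was pre-specified and which was added. Elsewhere the SAP does label decisions as post-hoc, for example the catastrophic-HO cut-offs (1.10.2) and its preference for the untransformed analysis (2.4.4). It does not do so here.

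**Working it through.** The documents give no power or sample size for a secondary endpoint, so there is no stated figure to reproduce. The check has two parts.

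**1. Which analyses does Month 12 actually govern?**

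| Endpoint | Protocol 8.5.2.2 | SAP 2.4.4 | Limited to Month 12? |
|---|---|---|---|
| Any new HO; number of regions | Compound Poisson | theta1,1 from the primary model, posterior probability above 0.975 | Label only. SAP 2.1.3 says the primary endpoint uses new HO to Month 24 in MOVE and Month 36 in the NHS |
| Any new HO | not named | Exact test | Yes |
| Number of regions | not named | Negative binomial regression | Yes |
| Proportion with flare-ups | Bayesian Poisson | Exact test | Yes, through 2.1.3; 2.4.4 names no time point and no Part A comparison |
| Flare-up rate | Bayesian Poisson | Negative binomial with follow-up offset | No; through Month 24 |

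The two rows marked as not named are additions; SAP 1.10.3 says V1.2 added analyses for the HO-based secondary endpoints. The same section says the flare-up analyses were simplified, which is where the Bayesian Poisson method was dropped.

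**2. How much does the time point change the quantity?**

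Inputs from SAP 1.7: 0.707 regions with new HO per subject-year, SD 1.11 (check: 46/65 = 0.708), and a 30% planned reduction in regions. Counts follow a gamma-Poisson (negative binomial) model with size k, and mu is the mean count by the given time:

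P(any) = 1 − (k/(k + mu))^k

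The SD can be read in two ways:
- As the SD of subject-level rates, as in the SAP's simulation: k = (0.707/1.11)² = 0.406.
- As the SD of observed counts: k = 0.707²/(1.11² − 0.707) = 0.952.

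The values of mu are 0.707 and 1.414 untreated (Months 12 and 24), and 0.495 and 0.990 treated.

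| | Month 12 untreated / treated | Difference | Month 24 untreated / treated | Difference |
|---|---|---|---|---|
| k = 0.406 | 33.6% / 27.6% | 6.0 | 45.6% / 39.4% | 6.2 |
| k = 0.952 | 41.1% / 32.9% | 8.2 | 58.0% / 49.3% | 8.7 |

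Status changes between the two times: 45.6 − 33.6 = 12.0 points untreated and 39.4 − 27.6 = 11.8 treated with the first k; 16.9 and 16.4 with the second. The risk ratio moves from 0.82 to 0.86, or from 0.80 to 0.85.

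Power of the region-count regression, with 90 NHS and 80 MOVE subjects, rate ratio 0.7 and one-sided 2.5%:

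Var(log RR) = [1/(0.707·T_NHS) + 1/k]/90 + [1/(0.495·T_MOVE) + 1/k]/80

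Power = Φ(0.357/SE − 1.96), where 0.357 = −ln 0.7.

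| Follow-up in years (NHS, MOVE) | k = 0.406: SE, power | k = 0.952: SE, power |
|---|---|---|
| 1, 1 (Month 12) | 0.315, 20% | 0.256, 28% |
| 1.75, 1.3 (left after the dosing cut) | 0.294, 23% | 0.231, 34% |
| 1.75, 2 (as planned) | 0.283, 24% | 0.215, 38% |

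The NHS figure is (45·1.5 + 45·2)/90 = 1.75. The MOVE 1.3 years is an assumption. The planned pattern at the second interim in SAP Table 7 gives (45·1 + 35·1.5)/80 = 1.2, for which power is 22% or 33%. The roughly 45 subjects expected in both groups are treated as independent, so the power figures are illustrative.

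**The case against.** The strongest reply is that little is lost. For the key secondary and the region count, the protocol's named method is kept, it is the secondary analysis with a stated significance rule, and it uses every interval. The Month 12 exact test and regression are extras that the protocol never promised. Month 12 is the first scan time shared by both studies (NHS at 12, 24 and 36; MOVE at 6, 12, 18 and 24), and a crude proportion ever affected would be distorted by unequal follow-up. Descriptive tables run by visit and overall, and at the third interim the secondary analyses are also run on all timepoints. SAP 1.10.3 does disclose that timepoints were added.

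Most of this stands. A reader might infer that the protocol-defined key secondary is never tested, or that later scans are thrown away. The documents do not support either: theta1,1 covers both HO endpoints with the longer data.

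Some of it does not stand. The scan-schedule rationale appears nowhere in the SAP, and Month 24 is also a shared scan time. Unequal follow-up calls for an offset, which the SAP already uses for the flare-up rate. Descriptive tables are not comparisons. Saying that timepoints were added does not tell the reader that the result departs from the protocol. The retained Bayesian test does nothing for the flare-up proportion.

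**Conclusion.** The two documents conflict on the time frame of three secondary endpoints, including the key secondary. The SAP's version was added after unblinding and is not declared as a departure. The practical reach is narrow: a wrong label on the theta1,1 test, two added comparisons restricted to Month 12, and a flare-up proportion with no specified Part A comparison.

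The endpoint itself changes materially: about 12 to 17 points of subjects in each group switch status between Months 12 and 24, depending on how the SD of 1.11 is read. The treatment contrast hardly changes (6.0 to 6.2 points, or 8.2 to 8.7). Region-count power rises only from about 20% to 23%, or from 28% to 34%, with the follow-up assumed to remain after the cut.

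A reader might also infer that Month 12 was picked because it favoured palovarotene. Nothing in the documents or in the planning model shows that it favours either group. These sizes rest on the planning rate, the planned 30% reduction and a constant rate over time. They do not describe the observed data, and they say nothing about flare-up rates.

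**What to change.** 1. In SAP 2.4.4, remove the Month 12 label from the theta1,1 test and state that it covers all Part A follow-up up to the dosing cut.
2. Add Part A comparisons up to the cut. For the region count, use negative binomial regression with a log follow-up offset. For the any-new-HO and flare-up proportions, use a complementary log-log model with a log follow-up offset. That offset is exact only for a constant rate common to all subjects, so also give the proportion implied by the fitted negative binomial model as a check. Report these beside the Month 12 results, and identify the Part A version as the protocol-defined one.
3. In SAP 1.9 and 1.10.3, state that the Month 12 time point was added after unblinding and departs from the protocol. If the common scan schedule was the reason, say so.

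Estimates over Parts A and B are left out of this fix, because SAP 1.9.3 limits the document to Part A.

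The cost is a few model runs on existing data and some SAP wording. Month 12 stays in the report but no longer stands alone as the defined endpoint. Because SAP 3.3 does not plan to rerun interim-report analyses for the final report, the additions have to be requested explicitly.
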